4.1.2 Scientific Rationale for Study Design

This is a multi-center, open-blind study assigned randomly to 2 treatments (HemoStyp or Surgicel) in a 1:1 ratio. This study is designed to compare HemoStyp with Surgicel, which represents the current standard of care for control of mild to moderate bleeding in an intra-operative setting.

The primary outcome measure for this study is the median time to achieve hemostasis. This is a clinically appropriate outcome measurement in a surgical setting and will assess the whether HemoStyp is non-inferior to Surgicel in terms of the key parameter of median time to achieve hemostasis at target bleeding sites. This study will also evaluate the categorical parameters, namely the percentage of subjects achieving hemostasis at pre-specified time intervals (30 second intervals from application through 10 minutes). In addition, this study appropriately evaluates the percentage of subjects with re-bleeding events during surgery and any post-surgical events requiring additional surgery during a 30-day follow-up period.

4.1.3 End of Study Definition

A participant is considered to have completed the study if he/she has completed the surgery and follow-up visit shown in [Table 1.1 Schedule of Evaluations](#). The end of the study is

defined as the date of the last scheduled procedure was performed for the last participant in the trial.

5 STUDY ENDPOINTS

5.1 Primary Endpoint

The primary performance endpoints include:

- Time to hemostasis from start of study treatment at target bleeding site until 10 minutes after treatment initiation.

5.2 Secondary Endpoints

Secondary efficacy endpoints include:

- Percentage of subjects achieving hemostasis at the target bleeding site at 2 minutes, 5 minutes and 10 minutes following the start of study treatment;
- Percentage of subjects with intraoperative hemostasis at the target bleeding site;
- Percentage of subjects with intraoperative re-bleeding from the target bleeding site post hemostasis; and
- Postoperative re-bleeding from the target bleeding site requiring surgical re-exploration up to 30 days after surgery.

5.3 Safety Assessments

Safety assessments will include evaluation of the frequency and nature of adverse events (AEs) and adverse device effects (ADEs) up to 30 days after treatment application.

6 SELECTION OF STUDY POPULATION

6.1 Inclusion Criteria

Subjects will be eligible to participate in this study if they meet all of the following criteria:

1. Elective procedure (non-laparoscopic thoracic, abdominal, or vascular surgery);
2. At time of surgery has mild to moderate soft tissue, vascular or parenchymal bleeding present at target bleeding site after primary standard conventional surgical hemostatic methods are proven to be ineffective or impractical;
3. Ages: Adult subjects ≥ 18 years of age; and
4. Subjects who are willing and able to sign consent.

6.2 Exclusion Criteria

Subjects will not be eligible to participate in this study if they meet any of the following criteria:

1. Physical or psychological condition which would impair study participation;
2. Indications for emergency surgery;

3. Pre-operative laboratory findings of a hematologic disorder;
4. Subjects with history of moderate to severe allergies;
5. Subjects undergoing minimally invasive laparoscopic surgery;
6. Subjects who will require platelet or fresh frozen plasma transfusion during surgery;
7. Subjects who are pregnant or breast-feeding at the time of surgery; or
8. Subjects on P2Y12 platelet inhibitor (Plavix) less than 5 days prior to surgery, warfarin or Xa inhibitors not withheld per standard protocols for the management of anticoagulants pre-operatively.
9. Patients with a coagulation disorder, thrombocytopenia, liver disease and anti-thrombin therapy.

6.3 Screen Failures

All subjects signing the informed consent who do not have mild to moderate soft tissue, vascular or parenchymal bleeding (based on validated scale [Lewis 2017]) present at target bleeding site after primary standard conventional surgical hemostatic will be recorded as screen failures. The relevant electronic Case Report Form (eCRF) pages (demographics, reason for screen failure) will be completed for all screen failure subjects and the data will be included in the study database.

6.4 Removal of Subjects from Study

In accordance with the current revision of the Declaration of Helsinki and the Code of Federal Regulations, a subject has the right to withdraw from the study at any time for any reason without prejudice to his/her future medical care by the physician or the institution. Should a subject (or subject's legally authorized guardian/representative) decide to withdraw; all efforts will be made to collect any adverse events they have experienced, if applicable. Subjects who withdraw or are terminated early from the study may be replaced. Participation may be terminated prior to completing the study for any of the reasons listed below (reasons that do not fit the categories below will be documented as "other").

Withdrawal of Consent:

If a subject chooses to withdraw early from the study, the eCRF completion page should be completed. When a subject's participation is terminated prior to completing the study, the reason for withdrawal is to be documented on the eCRF and in the source documentation.

Surgical:

The Investigator must withdraw a subject intraoperatively for the following reasons:

- Subjects do not have an appropriate target bleeding site.
- Subject develops coagulation diathesis post-operatively such as DIC (Disseminated Intravascular Coagulation).

Death:

When possible, the cause of death will be documented.

Lost to Follow-up:

All subjects should be encouraged to return for protocol required clinic visits for evaluation during the study follow-up period. If a patient is unable to return for a clinic visit or unable to be contacted by telephone, attempts to contact the patient should be documented in the source documents. Only after failing to contact the patient at the final follow-up visit, the patient will be considered lost to follow-up and the primary reason for early termination will be completed in the eCRF.

Site Termination or Study Termination:

The Sponsor may terminate a site or study at any time. When this occurs all subjects at the site will be withdrawn and documented as early termination. Reasons for site or study termination may include, but are not limited, to the following:

- Administrative concerns (e.g., inadequate patient enrollment, investigator/institution non-compliance, change of business strategy, etc.).
- Safety issues, including reaching any of the complication thresholds, including those due to non-compliance, which substantially affect the risk-to-benefit ratio of the study subjects at a site or for the study as a whole.
- Futility: It is evident that the endpoint cannot be reached given the trial design and number of enrolled participants.
- Regulatory body mandates.

The Investigator has the right to terminate their participation at any time. Should this be necessary, procedures for termination will be provided by the Sponsor.

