11.1 Determination of Sample Size

A non-inferiority comparison will be performed to determine if the hazard ratio with an overall sample size of 212 subjects (106 HemoStyp group and 106 Surgicel group) achieves 80% power at a 0.05 significance level when the hazard ratio is actually 1.33 (median survival is 3.0 minutes for HemoStyp and 4.0 minutes for Surgicel). The non-inferiority ratio is 0.75 (corresponding to margin of 1 minute). It is anticipated that the proportion of subjects observed with the event during the study is 0.90 for the HemoStyp group and 0.92 for the Surgicel group. These results assume that the hazard ratio is constant throughout the study and that Cox proportional hazards regression or the non-inferiority log-rank test is used to analyze the data.

It is anticipated that approximately 710 subjects will be screened to randomize approximately 236 subjects with an anticipated drop-out rate of approximately 10%.

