11.2.2 Analysis Populations

Intent-To-Treat Population (ITT): The ITT population will include all subjects who are randomized to HemoStyp or Surgicel. The efficacy analysis will be performed using the ITT population.

The Per Protocol population (PP): The PP population will include all subjects who are not major protocol violators with regards to inclusion/exclusion criteria, randomization, and have availability of scheduled data for all treatments and efficacy evaluations.

Safety Population: The safety population will include all subjects who are treated with any amount of HemoStyp or Surgicel. Safety analyses will be performed using the safety population and subjects will be analyzed according to the treatment they actually receive.

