11.2.5 Efficacy Analyses

Primary Endpoint

The time to hemostasis will be measured from start of study treatment to the achievement of hemostasis at the target bleeding site (TBS), or to the end of the 10-minute observation period. The time to hemostasis will be considered as censored at the end of the 10-minute observation period. Time to hemostasis will be quantified in minutes according to its nominal time point. When re-bleeding occurs, and the cessation of bleeding is again achieved at a later time point, the effective time to hemostasis will be the latter time point. The time to hemostasis will be the time from start of study treatment to that last effective hemostatic time point.

Secondary Endpoints

- Percentage of subjects achieving hemostasis at the target bleeding site at 2 minutes and at 5 minutes following the start of study treatment;
- Percentage of subjects with intraoperative hemostasis at the target bleeding site;
- Percentage of subjects with intraoperative re-bleeding from the target bleeding site post hemostasis;
- Postoperative re-bleeding from the target bleeding site requiring surgical re-exploration up to 30 days after surgery.

Analysis of the Primary Endpoint

The primary endpoint analyses will be based on ITT population. The primary analysis is the test of non-inferiority of HemoStyp compared with Surgicel. Cox proportional hazards regression or log-rank test will be used for the analysis of non-inferiority.

The null hypothesis for the testing of the primary endpoint is described below:

H0: HemoStyp is inferior or worse than Surgicel by more than 1 minute for median survival (HR<0.8);

H1: HemoStyp is inferior to Surgicel by less than 1 minute for median survival (HemoStyp is not inferior to Surgicel) ($HR > 0.8$);

If the lower bound 95% confidence interval of $HR > 0.8$, we conclude that HemoStyp is not inferior to Surgicel.

The primary endpoint analyses will also be performed on the PP population.

Analyses of Secondary Endpoints

A two-sided z-test with pooled variance will be used to test the difference for each secondary endpoint. The 95% confidence intervals (CIs) for each secondary endpoint in each group (HemoStyp or Surgicel) will be provided.

Secondary endpoints will be assessed at significant level of 0.05 in the order listed below after achievement of a significant result for the primary endpoint:

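### Section 6.4 lets randomised subjects be replaced without a cap, although the 236 to be randomised already includes the 10% drop-out allowance

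*Combined protocol and SAP*

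**What the plan says.** **Replacement.** Section 6.4: "Subjects who withdraw or are terminated early from the study may be replaced". The section gives no maximum, no decision-maker, no cut-off relative to randomisation and no rule for analysing a replaced subject. The reasons it lists are:
- withdrawal of consent;
- two surgical reasons: "Subjects do not have an appropriate target bleeding site", and a coagulation problem that the text describes as developing post-operatively;
- death;
- loss to follow-up, which is declared only after contact has failed at the final visit;
- closure of a site or of the study, in which case every subject at the site is withdrawn.

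**Sample size.** Section 11.1 states that an "overall sample size of 212 subjects (106 HemoStyp group and 106 Surgicel group) achieves 80% power at a 0.05 significance level", and describes the numbers "screened to randomize approximately 236 subjects with an anticipated drop-out rate of approximately 10" percent. The synopsis gives 236 as the number of subjects but 234 randomised in its statistical row. Section 4.1 gives 234 randomised and 236 enrolled.

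**Analysis sets.** Section 11.2.2: "The ITT population will include all subjects who are randomized to HemoStyp or Surgicel". Section 11.2.7 restricts all analyses to subjects in whom one of the two products was applied, and rules out imputation.

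**Setting.** The trial is open-label (section 4.1) and allocates by sealed envelope (section 4.1.1). The primary endpoint closes 10 minutes after treatment starts (section 5.1).

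**The concern.** A drop-out allowance and a replacement rule are two ways of meeting the same need, and either one alone delivers the 212 subjects. Having both means that the number randomised is not fixed by the plan.

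The reasons in 6.4 clearly reach treated subjects. Loss to follow-up can be declared only at the end of the 30-day period. The coagulation item is described as post-operative. Site closure sweeps in everyone at the site, including subjects whose primary data are complete. Replacing such a subject restores no primary outcome and cannot recover that subject's missing 30-day data.

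Two things are at stake. First, enrolment can be extended subject by subject while arms and outcomes are visible at the sites. Second, a narrower gap affects the comparison itself. A subject whose envelope has been opened but who is withdrawn before application belongs to ITT under 11.2.2, yet 11.2.7 leaves that subject out of every analysis. If a replacement is then enrolled and analysed, one subject has been substituted for another after allocation was known.

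**Working it through.** **Inputs.** 212 subjects for power, about 10% drop-out and about 236 randomised (section 11.1); 234 randomised (synopsis and section 4.1); 10 to 15 sites (synopsis). The 212 is taken as stated. Whether it follows from its own hazard ratio and margin is a separate question that does not affect this step.

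**1. Reproduce the plan's figure.** 212 / (1 − 0.10) = 235.6, rounded up to 236. The other figure is consistent with 212 × 1.10 = 233.2, rounded up to 234. Both totals therefore carry the allowance.

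**2. Is the allowance enough without replacement?**
- 236 × 0.90 = 212.4, which meets 212.
- 234 × 0.90 = 210.6, which falls short by one or two subjects.

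**3. Replacement alone, without the allowance.** A target of 212 completers at 10% loss needs 212 / 0.90 = 235.6 randomised. This is the same total, so the two provisions are alternatives.

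**4. Both provisions, every loss replaced, 10% loss.**
- Each loss replaced once: 236 + 0.10 × 236 = 259.6, about 260. Evaluable: 259.6 × 0.90 = 233.6, about 234.
- Replacement until 236 complete: 236 / 0.90 = 262.2, about 262. Evaluable: 236.
- Excess randomised: 24 to 26, which is 24/236 = 10% to 26/236 = 11% above plan. Surplus evaluable: 234 − 212 = 22 to 236 − 212 = 24.

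**5. Other loss rates (assumptions; the plan gives only 10%), starting from 236.**

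| Loss | Randomised, each loss replaced once | Randomised, until 236 complete | Completers without replacement |
|---|---|---|---|
| 5% | 247.8 | 248.4 | 224.2 |
| 10% | 259.6 | 262.2 | 212.4 |
| 15% | 271.4 | 277.6 | 200.6 |
| 20% | 283.2 | 295.0 | 188.8 |

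**6. One site closure.** With equal enrolment across sites (an assumption), 236/15 = 15.7 to 236/10 = 23.6. About 16 to 24 subjects would become replaceable at once.

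**7. The two analysis provisions side by side.** For a subject randomised, withdrawn before application and then replaced:
- under 11.2.2 the subject is in ITT;
- under 11.2.7 the subject is in no analysis;
- the replacement, once treated, is in both.

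The documents do not say which provision prevails.

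**The case against.** The case on the other side is substantial.

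- **Replacement is optional.** A reader might infer that losses are certainly paid for twice. The text only permits replacement, and as a backstop for losses above 10% it would be reasonable: at 15% loss only 200.6 of 236 complete. This stands, and it makes the 24 to 26 an upper bound at 10% loss. However, the rule is not written as a backstop, and a late withdrawal does not reduce the primary data.
- **More subjects are not a bias.** A reader might infer an inflated type I error. Extra subjects do not cause that by themselves, and no such effect has been shown. Nothing in 6.4 lets anyone choose the replacement's arm, since the list is generated before the study starts and is stratified by centre. Nor do the documents name who decides on replacement, so they do not show that the choice rests with someone who knows the arm and the result. They also do not exclude it.
- **The target-bleeding-site item.** A reader might infer that 6.4 makes removal after randomisation an accepted route. The documents do not support that. Section 6.3 says that subjects without qualifying bleeding "will be recorded as screen failures", and sections 7, 7.2 and 8.7 make a suitable site a condition of randomisation. Replacing such subjects is screening attrition and does not draw on the 236. Only the wording of 6.4 needs aligning.
- **ITT as protection.** A reader might take it that ITT keeps both the withdrawn subject and the replacement. That holds under 11.2.2 alone. For an untreated subject, 11.2.7 contradicts it.

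**Conclusion.** The concern holds in a limited form. Section 6.4 gives an uncapped option to replace subjects, extending to those already randomised and treated, on top of a randomised number that already contains the 10% allowance. At the plan's own loss rate the excess is at most about 24 to 26 randomised subjects (260 to 262 in total), yielding about 234 to 236 evaluable. It would be wrong to read this as 260 subjects needed to obtain 212: 236 already does that.

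The size rests on three assumptions: the loss is 10%, every loss is replaced, and losses reduce the evaluable number at all. The last is doubtful for withdrawals after the 10-minute window.

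The more important consequences are not numerical. Final enrolment is discretionary in an open-label trial, and the conflict between 11.2.2 and 11.2.7 would let a subject withdrawn between allocation and application be omitted and substituted. This is a moderate weakness that should be corrected. It does not undermine the design.

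**What to change.** 1. In section 6.4, replace the permissive sentence with: *Randomised subjects will not be replaced; the 10% allowance in 11.1 covers losses.* Subjects not yet randomised can still be made up through screening.
2. Use 236 as the randomised number in the synopsis and sections 4.1 and 11.1, because 234 falls just short of 212 after a 10% loss.
3. Reconcile section 11.2.7 with section 11.2.2 so that every randomised subject stays in the ITT analysis, and state how a randomised but untreated subject is handled for the primary endpoint.
4. As a minor alignment, reconcile the target-bleeding-site item in 6.4 with sections 6.3, 7, 7.2 and 8.7, which already place that check before randomisation.

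A subject's right to withdraw consent is unaffected; the change concerns replacement and analysis only. The cost is a few sentences. Planned power is kept at the stated 10% loss (236 × 0.90 = 212.4), and no more subjects are needed than the 236 already planned.

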9.8 Reporting Adverse Events

The Investigator is required to report all adverse events experienced by the patient from the day of the surgical procedure (Visit 2) until the patient completes Visit 3 (30 days after the surgical procedure) or withdraws early (prior to Visit 3). All adverse events (both serious and non-serious), regardless of their relatedness to the study device or procedure, must be reported in the Adverse Event eCRF. The investigator will evaluate the severity of the event, and its relatedness to the study device or procedure. Both severity and relatedness of all adverse events need to be entered in the Adverse Event eCRF.

Any necessary medical management of the event will be recorded in the patient's medical record/source document. All adverse events must be followed until resolution or until they become stable but ongoing.

The Investigator will record all adverse events (both serious and non-serious) in the source documents. Standard medical terminology should be used when recording adverse events. In addition, the following information should be recorded:

- Onset date
- Resolution date or date of death
- Severity of the event
- Action taken
- Event status (ongoing at study end or resolved)
- Relationship of adverse event to the device used in the study
- Relationship of the adverse event to the study surgical procedure
- Indication of whether the event is serious.

Data related to SAEs will be collected until event resolution, or until the event is considered stable, or until all attempts to determine the resolution of the event are exhausted. All adverse events that are unresolved at study completion (or early termination) will be recorded as ongoing at study end.

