9.8.1 Procedures for Reporting Serious Adverse Events to the Sponsor

All SAEs that occur during the course of the study regardless of causality must be reported by the Investigator **within 24 hours** from the point in time when the Investigator becomes aware of the SAE. The SAE form should be submitted to the study medical monitor.

All serious adverse events, regardless of causality, should be collected and reported beginning with signing of the ICF through the follow-up visit.

Any SAEs that occur after the End of Study Follow-up Visit has concluded, including after the study has concluded, and that are **considered related to the study device or procedure by the Investigator** are considered reportable, and must be reported to the Sponsor **within 24 hours**.

The information collected by the site will include a minimum of the following: subject number; a thorough description (narrative) of the event, including its onset, relevant signs/symptoms, progression, treatment and outcome; and an assessment by the Investigator as to the severity of the event and relatedness to any/all study device(s) or study procedure(s).

The information reported on the SAEs report form should match the data provided by the site on the eCRF. The Investigator is also responsible for spontaneously reporting any subsequent follow-up information, including clinically relevant additional information, such as change in outcome.

In the event of death, the Investigator must report all available information to the Sponsor.

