11.2.7 Handling of Missing Data

All analyses will be performed only on subjects undergoing surgical procedures during which treatment (HemoStyp or Surgical) is applied to target bleeding sites. There will be no imputation of missing data for any parameters or for early terminated subjects.

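### Section 6.4 contradicts itself on withdrawal for post-operative coagulopathy and, if the post-operative wording is followed, can end 30-day data collection after an outcome-related event

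*Combined protocol and SAP*

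**What the plan says.** Under its Surgical heading, Section 6.4 opens with "The Investigator must withdraw a subject intraoperatively for the following reasons" and gives two reasons. The first is the lack of a suitable target bleeding site. The second is "Subject develops coagulation diathesis post-operatively such as DIC". The same section says "Subjects who withdraw or are terminated early from the study may be replaced". For subjects who choose to leave, it adds that "all efforts will be made to collect any adverse events they have experienced, if applicable".

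Three other sections govern what happens to the data:

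- Section 9.8 has the investigator report adverse events from the day of surgery "until the patient completes Visit 3 (30 days after the surgical procedure) or withdraws early (prior to Visit 3").
- Section 9.8.1 says "All serious adverse events, regardless of causality, should be collected and reported beginning with signing of the ICF through the follow-up visit".
- Section 11.2.7 says "There will be no imputation of missing data for any parameters or for early terminated subjects".

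On populations, Section 11.2.2 says "The ITT population will include all subjects who are randomized to HemoStyp or Surgicel". It defines the Safety population as everyone treated with any amount of either product, and makes Per Protocol membership depend on scheduled efficacy data being available.

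**The concern.** The lead-in places the withdrawal in the operating room, while the second reason arises only after the patient has left it. Sites have to guess which applies and may guess differently.

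Study product is applied during surgery (Sections 7 and 7.2), and the only scheduled study visit after that is Visit 3. A withdrawal after the operation therefore stops no study treatment. What it can stop is observation. The trigger occurs after randomisation, and a new coagulopathy plausibly bears on re-bleeding. That link is an inference, although the protocol treats coagulation disorders as important enough to exclude at entry (Section 6.2). Re-bleeding that requires re-exploration within 30 days is a secondary endpoint (Section 5.2). If follow-up ends because of such an event, the missing outcomes are unlikely to be missing at random.

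**Working it through.** **1. The two readings of Section 6.4.** If the lead-in governs, an event that arises after surgery triggers no withdrawal and the 30-day question does not arise. If the second reason governs, withdrawal after surgery is mandatory. The documents do not settle which is meant. The steps below follow the second reading.

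**2. What is kept and what can be lost, on that reading.**

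| Item | Text | Result |
|---|---|---|
| ITT and Safety membership | 11.2.2: all randomised; all treated | Kept |
| The coagulopathy, and re-bleeds or adverse events up to withdrawal | 9.8 | Kept |
| Later non-serious adverse events | 9.8: reporting ends at early withdrawal | Lost |
| Later re-exploration, as a serious adverse event | 9.8.1: through the follow-up visit | Uncertain; withdrawn subjects are not addressed |
| Later re-exploration, as the endpoint | 7.3 describes monitoring to Day 30 but does not mention withdrawn subjects; 11.2.7: no imputation | Can be lost |
| Per Protocol membership | 11.2.2: scheduled data available | Possibly lost |

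The undertaking in Section 6.4 to collect adverse events is written for subjects who decide to leave, and covers events already experienced. It does not cover later events or a withdrawal imposed by the investigator.

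**3. Which endpoints are exposed.** The primary endpoint closes 10 minutes after application (Section 5.1), and the intraoperative secondary endpoints are also complete before a post-operative trigger. One efficacy endpoint remains: 30-day re-exploration, fourth in the testing order of Section 11.2.5.

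**4. The plan's own figure.** Section 11.1 needs 212 subjects and allows 10% drop-out: 212 / (1 − 0.10) = 235.6, rounded up to 236, which reproduces. That is 236 / 2 = 118 per arm. (The 234 found elsewhere is 212 × 1.10 = 233.2, rounded up.) Replacement thus comes on top of an existing allowance.

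**5. Weight of one lost event.** The documents give no re-exploration rate, so the rates are assumed. Expected events per arm = 118 × rate; share of one event = 1 / expected events.

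| Assumed rate | Expected events | Share of one event |
|---|---|---|
| 1% | 1.18 | 85% |
| 2% | 2.36 | 42% |
| 5% | 5.90 | 17% |

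**6. Illustration of expected loss.** Let c be the share of subjects with coagulopathy, r₁ their re-bleeding risk and r₀ the risk in everyone else. If every re-bleed in the coagulopathy group follows withdrawal and is missed, the fraction unseen is c·r₁ / [c·r₁ + (1 − c)·r₀]. Assumed ranges: c 0.5% to 3%, r₁ 20% to 50%, r₀ 1% to 2%.

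- Lowest: 0.005 × 0.20 = 0.0010; 0.0010 / (0.0010 + 0.995 × 0.02) = 5%. Expected loss per arm: 118 × 0.0010 = 0.1 events.
- Highest: 0.03 × 0.50 = 0.0150; 0.0150 / (0.0150 + 0.97 × 0.01) = 61%. Expected loss per arm: 118 × 0.0150 = 1.8 events.
- Between: c = 1%, r₁ = 50%, r₀ = 1% gives a true rate of 0.0050 + 0.0099 = 1.49% against 1.00% among those still observed. Expected loss per arm: 118 × 0.0050 = 0.6 events.

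If coagulopathy occurred in 3% of one arm and 1% of the other (r₁ = 50%, r₀ = 1%), the true difference would be 2.47% − 1.49% = 0.98 percentage points, and the observed difference would be zero. All of these are upper-end cases, since they assume that nothing is captured after withdrawal.

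**The case against.** The strongest reply is that the analysis populations already protect the trial. ITT is everyone randomised and Safety is everyone treated, and the restriction in Section 11.2.7 to subjects in whom product was applied does not exclude these subjects. A reader might infer from Section 6.4 that the subjects most likely to re-bleed are removed from the results. The documents do not support that: only information after withdrawal is at risk.

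Second, a re-exploration would ordinarily meet the definition of a serious adverse event in Section 9.1, and Section 9.8 requires existing adverse events to be followed until resolved or stable. This stands in part. Section 9.8.1 is silent on withdrawn subjects, and a safety report is not the planned assessment of the endpoint.

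Third, few subjects are likely to be involved, because surgery is elective and coagulation disorders are excluded at entry. That is fair, and the 42% in particular must not be read as an expected loss.

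Two further inferences are tempting. One is that replacement biases the comparison. Section 6.4 only permits it, and under Section 11.2.2 the randomised subject stays in ITT, so a replacement adds to the total. With a 10% allowance already made, it is redundant but not shown to be harmful. The other is that the open-label design leads to uneven labelling of coagulopathy between arms. The trigger has no objective criteria, so this is possible, but nothing in the documents shows it.

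**Conclusion.** The concern holds in a limited form. The contradiction within Section 6.4 is plain on the page. On the post-operative reading, the plan makes withdrawal mandatory after an event plausibly related to outcome, and has no text that keeps the subject under observation to Day 30. The exposure is one rare secondary endpoint, later non-serious adverse events and possibly Per Protocol membership. The primary endpoint is unaffected, since each such subject's 10-minute result is already recorded.

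The size cannot be determined from the documents. The shares of 85%, 42% and 17% rest on assumed rates and show only how heavily one event would weigh. The 5% to 61% range rests on further assumed rates and on complete loss after withdrawal. The point merits a change because a stated rule, and not a mere gap in detail, creates the informative missingness, and because the remedy costs almost nothing.

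**What to change.** - Reconcile the lead-in and the second reason in the Surgical part of Section 6.4. Which timing is intended is for the sponsor to state.
- Add to Sections 6.4 and 9.8 that an event after application of study product does not end data collection: re-bleeding, re-exploration and adverse events are recorded to Visit 3 unless the subject withdraws consent.
- Say in Section 9.8.1 that serious adverse event reporting through the follow-up visit also covers subjects withdrawn by the investigator.
- Leave the analysis populations of Section 11.2.2 as they are. State that any replacement adds to, and does not substitute for, a randomised subject.

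The cost is protocol wording. Visit 3 is already scheduled for every subject. The change concerns data collection and analysis only, not patient care.
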